trial to evaluate the effectiveness of a clinic-based HIV Active Linkage, Engagement, and Retention to Treatment (ALERT) specialist on improving endpoints of retention in care and maintenance of antiretroviral therapy (ART) as compared to the current standard of care (SOC) in HIV primary

care clinics.

Duration: Each subject will receive follow-up of at least 48 weeks. Follow-up for

enrolled patients will continue until the last enrolled patients has been

on study for 48 weeks

Sample Size: A total of 300 subjects will be randomized, 150 per arm.

Study Population: Eligible subjects will include 1) newly diagnosed HIV-infected individuals

entering primary HIV care at one of the CCTG clinics, or 2) previously diagnosed HIV-infected individuals who are "out of care" defined as having no visit with a prescribing HIV provider in the last 180 days and

not on a stable ARV regimen.

Stratification: Subjects will be stratified based on study site and if they are newly

diagnosed or returning to care. (See Diagram 1)

Intervention: Subjects will be randomized (1:1) to either the ALERT Enhanced Retention

Intervention Arm or the SOC Arm. Subjects placed into the ALERT Intervention Arm will receive aggressive engagement efforts by the ALERT specialist to ensure visit continuity and retention into care. The ALERT specialist will also administer an education intervention consisting of 5 retention modules designed to improve HIV knowledge and self-efficacy, and will also monitor health care visits and intervene via

methods to track, find, and re-engage patients during the study. Patients placed into the SOC arm will receive the HIV care clinic's current standard

[figure not shown]
of care retention services.

Outcomes:

Primary Outcome: Time to "lost to follow up" (LTFU) defined as the time from study entry to

no visit with a prescribing HIV provider in the last 180 days

DIAGRAM 1: CCTG 594 STUDY SCHEMA

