9.4 Sample Size and Accrual

9.4.1 Power and Sample Size Justification

The primary outcome for this study is to compare the time to LTFU. A secondary outcome is time to initiation of ART. Sample size calculations were based on a two-sided, two-sample log-rank test to compare the differences in time to the-primary endpoint proportions between the intervention arm and the standard of care arm.

Since attrition is a component of the composite endpoint, attrition rates are not used as an adjustment in the power calculations. Assuming 150 subjects per group in each of the two

Table 5: Power based on a two-sided, log-rank test with alpha=0.05 and N=150 per arm (total N = 300)							
Composite	Composite rate	Corresponding	Statistical				
rate without	without	Hazard Ratio	Power (%)				
Endpoint in	Endpoint in	(HR)					
SOC (%)	Intervention						
	(%)						
65	80	1.93	82				
65	85	2.65	97				
70	85	2.19	87				
75	87.5	2.15	78				
75	90	2.73	92				
80	92.5	2.86	87				
80	95	4.35	97				

groups (for a total of 300 subjects), we have 87% power to detect a difference of 15%, assuming a time without a composite endpoint rate of 70% in SOC arm and that the intervention arm will increase the time without an endpoint (to a rate to 85%). This corresponds to a hazard ratio of 2:19. Table 5 shows other possible standard of care rates between arms (and hazard ratios), and corresponding statistical power. The calculations assume that the hazard rates are proportional.

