9.6 Analyses

9.6.1 Statistical Analysis Plan

In general, analyses will incorporate the intent-to-treat principle, namely, all randomized participants will be included in the analysis. The primary analysis compares the ALERT Intervention to the SOC arm. For all secondary analyses of interest, no adjustments for multiple comparisons will be made, and a p-value of 0.05 will be considered statistically significant. Demographic and baseline measurement variables will be summarized via standard descriptive statistics.

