9.6.3 Analysis of Secondary Outcomes

Main Secondary Outcome: The CCTG 594 secondary outcome is time to initiation of ART. A survival analysis of time to initiation of ART will be conducted. Time to initiation of ART will be calculated as total days between the first visit to the ART start date. For those participants who do not start ART, the time to initiation of ART will be censored to the participant's last visit date.

The NULL hypothesis is that the median time to initiation of ART estimated using the Kaplan-Meier method will be identical in both groups. The log-rank test will be used to test the null hypothesis against the alternate hypothesis that the median time to initiation of ART is not the same between the groups.

In addition, to assess the factors associated with time to initiation of ART, Cox regression models will be performed on two subgroups, looking at each arm separately. The model will have time to initiation of ART as the outcome, baseline variables such as demographic, socioeconomic, psychosocial factors, risk behavior, substance use and psychiatric illness as predictors.

9.6.4 Other Secondary Analyses

Descriptive analyses will be conducted for all the secondary analyses including comparisons between randomized groups on the following measures:

- Baseline and follow-up scores on HIV and health literacy assessments, disclosure rates, adherence, and measures of selfefficacy
- Number of primary care visits per year
- HIV RNA < 50 and <200 copies/mL at years 1 and 2
- CD4 cell counts and changes from baseline in CD4 at years 1 through 2
- Scores on Beck Depression Index
- Substance use
- HIV high-risk transmission behaviors
- Time to AIDS diagnosis or death
- Reasons eligible patients decline study participation

For patients who meet the primary endpoint (LTFU) but subsequently return to care, secondary analyses will measure the proportion returning in the intervention vs. SOC arm and the time between their last and return visit with a prescribing provider.

Fisher's exact test will be used for categorical variables; T-test (or Wilcoxon Rank Sum test, if parametric assumptions fail) will be used for continuous variables.

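### Year 2 comparisons of CD4 and annual scores use single-time-point tests on the earlier enrollees alone, and so are less precise than the collected data allow

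*Combined protocol and SAP*

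**What the plan says.** Section 9.6.4 lists between-arm comparisons that include "CD4 cell counts and changes from baseline in CD4 at years 1 through 2", HIV RNA below 50 and 200 copies/mL at years 1 and 2, and baseline and follow-up scores. It names no year for the scores. That they are annual comes from section 1.3.4 and from the yearly study visits in section 6.2.4.

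The methods are Fisher's exact test for categorical variables, while "T-test (or Wilcoxon Rank Sum test, if parametric assumptions fail) will be used for" continuous ones. The available text describes no longitudinal model, baseline adjustment or missing-data method for these measures. Section 9.0 refers to a statistical analysis plan that gives details and takes precedence, but no separate plan is included in the combined document.

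On follow-up, the Schema (Duration) guarantees 48 weeks and says that follow-up for "enrolled patients will continue until the last enrolled patients has been" on study for that long. Table 1 (section 6.1, note 5) allows annual visits and labs 60 days either side of the due date.

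**The concern.** A t-test or Wilcoxon test at Year 2 uses only patients with a Year 2 value. Because follow-up closes on a common date, later enrollees cannot have one. Nearly all of them can have a Year 1 value, which is correlated with the Year 2 value they would have had, but the planned test makes no use of it. The test on raw values also ignores baseline, and the test on change uses baseline only by subtraction.

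At stake is the precision of the Year 2 arm differences in CD4 and psychosocial scores, which are the plan's evidence on whether an effect on those measures lasts. For HIV RNA, the plan does not say who is counted in the Year 2 denominator.

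A second, separate issue is missed annual visits. Section 6.2.4 lets a subject stay in the study after missing one. If missing Year 2 depends on earlier status, and does so differently by arm, an available-case test can be biased.

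**Working it through.** **The plan's own figure.** The only power statement concerns the primary endpoint (section 9.4.1): "Power based on a two-sided, log-rank test with alpha=0.05 and N=150 per arm (total N = 300"), where "we have 87% power to detect a difference of 15" percentage points, "assuming a time without a composite endpoint rate of 70% in SOC arm", and "This corresponds to a hazard ratio of 2:19".
- Hazard ratio = ln(0.70)/ln(0.85) = 2.195.
- Expected events = 150 × (0.30 + 0.15) = 67.5.
- Freedman power = Φ(√67.5 × 1.195/3.195 − 1.96) = 86.7%, which reproduces the stated 87%.

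No power or precision figure is given for CD4 or the scores, so there is nothing to reproduce for Year 2.

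**Who can have a Year 2 value.** The minimum follow-up is 48 × 7 = 336 days. Year 2 falls due on day 730, and its window opens on day 730 − 60 = 670. Enrolment must therefore precede the last enrolment by 670 − 336 = 334 days (window opening) or 730 − 336 = 394 days (due date). In weeks, with Year 2 at week 104, these are about 47.4 and 56.

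Assume uniform accrual over A weeks (the documents give no accrual period). The fraction f that can have a Year 2 value is (A − 47.4)/A at window opening and (A − 56)/A at the due date.

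| Accrual | Due date: f (N of 300) | Window opening: f (N of 300) |
|---|---|---|
| 52 weeks | 0 (0) | 0.09 (26) |
| 78 weeks | 0.28 (85) | 0.39 (118) |
| 104 weeks | 0.46 (138) | 0.54 (163) |
| 156 weeks | 0.64 (192) | 0.70 (209) |

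These are ceilings, before missed visits and withdrawals.

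**What Year 1 values add.** Let n be the number per arm with Year 1, f the fraction who also have Year 2, and r the Year 1 to Year 2 correlation. A likelihood-based model estimates the Year 2 mean with variance σ²[(1 − r²)/(nf) + r²/n]. The Year 2 test has variance σ²/(nf). The ratio is 1 − r²(1 − f). With Year 1 complete:

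| Accrual | Basis for f | r = 0.3 | r = 0.5 | r = 0.7 |
|---|---|---|---|---|
| 78 weeks | window opening | 0.95 | 0.85 | 0.70 |
| 104 weeks | window opening | 0.96 | 0.89 | 0.78 |
| 156 weeks | window opening | 0.97 | 0.92 | 0.85 |
| 78 weeks | due date | 0.94 | 0.82 | 0.65 |
| 104 weeks | due date | 0.95 | 0.87 | 0.74 |
| 156 weeks | due date | 0.97 | 0.91 | 0.82 |

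In terms of power, take 104-week accrual at the due date (about 69 per arm) and a difference of 0.323 SD, which 150 per arm would detect with 80% power. Power at Year 2 is 48% with the t-test and 50%, 53% and 60% with the model at r = 0.3, 0.5 and 0.7.

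**What baseline adds for change in CD4.** Assume all pairwise correlations equal r, and let n₂ be the number per arm with Year 2. In units of σ², the variances per arm are:
- change-score t-test: 2(1 − r)/n₂;
- baseline-adjusted Year 2 analysis: (1 − r²)/n₂, which is (1 + r)/2 of the change-score variance;
- baseline-adjusted model with Year 1: (1 − r²)[(1 − p²)/n₂ + p²/150], with p = r/(1 + r).

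For 104 weeks and r = 0.7 (n₂ = 69.2) these are 0.00867, 0.00737 and 0.00669. The last is 0.77 of the first. Over r = 0.5 to 0.8 and accrual of 78 to 156 weeks (due date), the full model has 0.69 to 0.84 of the change-score variance. Baseline adjustment alone gives 0.75, 0.85 and 0.90 at r = 0.5, 0.7 and 0.8. Year 1 values then take off a further 4% to 14%. Baseline is the larger part at r = 0.5 and 0.7. At r = 0.8 with accrual of 78 or 104 weeks, Year 1 adds slightly more than baseline.

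**The case against.** The strongest reply is about weight. Section 9.6.4 calls these analyses descriptive, section 9.6.1 leaves secondary analyses unadjusted for multiplicity, and the trial is powered only for time to loss to follow-up. The log-rank analyses of the primary and main secondary outcomes handle staggered follow-up by censoring. The planned tests are less efficient rather than invalid, and the gain is slight if r is near 0.3 or accrual is long. All of this stands. It limits the importance of the point but does not remove it, because 9.6.4 names tests for between-arm comparisons and 9.6.1 sets 0.05 as the significance level for secondary analyses.

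A separate analysis plan might already specify a longitudinal model. That cannot be excluded, and the point applies to the text as it stands.

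Four stronger readings are tempting, and the documents do not support them:
- **That the truncation biases the comparison of arms.** Whether Year 2 can be reached depends on enrolment date, and allocation is 1:1 throughout.
- **That bias from missed visits can be quantified.** Suppose about 30% drop out of standard care after Year 1, with odds 2.2 times lower under ALERT and a log-odds slope of 0.7 per SD of the Year 1 value. Simulation then gives available-case estimates of 0.23 to 0.27 for a true 0.30 SD, and the joint model recovers 0.30. None of those dropout parameters is in the documents. If dropout depends instead on the unseen Year 2 value, the joint model gives 0.21 to 0.25 against 0.20.
- **That 9.6.4 conflicts with 9.6.1.** The statement that "all randomized participants will be included in the analysis" is introduced as a general rule under intention to treat, and it does not require values from people not yet due for a visit.
- **That Year 1 data are thrown away.** They have their own comparison. What is lost is their contribution to the Year 2 estimate.

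**Conclusion.** The point holds as a loss of precision in secondary analyses. As written, the Year 2 comparison of continuous measures rests on a subset fixed by enrolment date and leaves usable information aside. With uniform accrual, complete Year 1 data and f taken at window opening, using Year 1 values gives 0.70 to 0.96 of the t-test variance at 18 to 24 months of accrual and 0.85 to 0.97 at 36 months, for r from 0.7 to 0.3. Taking f at the due date gives slightly larger gains. Accrual length and r are assumptions, so the size is a range.

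Bias from missed annual visits is possible, but the documents do not fix its amount. Year 2 is explicit for CD4 and HIV RNA and inferred from the annual schedule for the scores. The primary analysis is unaffected. This is a worthwhile, low-cost improvement and not a flaw that threatens the trial's main conclusion.

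**What to change.** - **Continuous annual measures (CD4 and scores).** Analyse each in one likelihood-based repeated-measures model with the baseline value, arm, year, arm-by-year interaction, the randomisation strata (clinic site; newly diagnosed or returning to care) and an unstructured within-patient covariance. Report the Year 1 and Year 2 arm differences from that model.
- **HIV RNA below 50 and below 200.** Use a repeated-measures logistic model, and limit the Year 2 denominator to participants whose Year 2 window opened before study close.
- **Reporting.** State the number per arm who could have reached Year 2 and the number with a value.

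The cost is a change of wording before analysis and slightly more analysis work, with no new visits, samples or patients. The model relies on data being missing at random given the observed values, and it would not remove bias if missingness depends on the unseen Year 2 value. Nor can it create Year 2 data: if accrual lasted less than about 47 weeks there would be none to analyse.

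### Section 9.6.4 gives no survival method, time origin or censoring rule for time to AIDS or death, and compares return to care without allowing for unequal follow-up after LTFU

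*Combined protocol and SAP*

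**What the plan says.** Section 9.6.4 (Other Secondary Analyses) lists measures for descriptive analysis, including comparison of the randomised groups. One is "Time to AIDS diagnosis or death", which is also a secondary objective (1.3.4.5). For patients who reach LTFU and later come back, the section compares by arm the proportion returning and "the time between their last and return visit with a prescribing provider". It closes with the only tests it names: Fisher's exact test for categorical variables, and "T-test (or Wilcoxon Rank Sum test, if parametric assumptions fail) will be used for continuous variables".

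Two other time outcomes are treated differently. Sections 9.6.2 (time to LTFU) and 9.6.3 (time to ART initiation) each give a start point, a censoring rule, Kaplan-Meier and the log-rank test.

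On duration, the Schema states: "Each subject will receive follow-up of at least 48 weeks". It adds that follow-up runs until the last patient enrolled has reached 48 weeks. Section 6.2.4 says patients stay under follow-up after LTFU for the secondary endpoints. Section 9.6.1 sets 0.05 as the significance level for secondary analyses, without multiplicity adjustment. The opening of section 9.0 says a SAP gives the details and takes precedence; no separate SAP text is in the documents supplied.

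**The concern.** Time to AIDS or death is a censored outcome, and early enrollees are watched longer than late ones. None of the three named tests handles censoring. An analyst working from section 9.6.4 alone has to reduce the outcome to yes/no, or treat the time as an ordinary continuous variable. The second route is the harmful one. Applied to observed times, a t-test or Wilcoxon partly compares lengths of follow-up. Applied to event times only, it asks when events happened among those who had one and drops the question of whether they happened.

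Return to care has a different weakness. A patient who reaches LTFU near study close has little time to come back, so the proportion returning depends partly on when LTFU occurred, which the intervention is meant to change. The gap among returners is conditional on two post-randomisation events, LTFU and return.

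At stake is the reading of two secondary comparisons. The primary analysis is not affected.

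**Working it through.** **1. The plan's own power figure.** Table 5 is headed "Power based on a two-sided, log-rank test with alpha=0.05 and N=150 per arm (total N = 300"). For 70% against 85% without the endpoint:
- HR = ln(0.70)/ln(0.85) = 2.19.
- Expected events = 150 × 0.30 + 150 × 0.15 = 67.5.
- Freedman power = Φ(√67.5 × (2.19 − 1)/(2.19 + 1) − 1.96) = 86.7%, against the stated 87%.

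All seven rows of Table 5 reproduce within one point. The plan states no power for the outcomes discussed here, so the rest rests on assumptions.

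**2. AIDS or death, assumed 12-month risks.** Inputs from the plan: 150 per arm, two-sided 0.05, at least 48 weeks of follow-up. Assumed: exponential times, and extra follow-up uniform over 0 to 12 months. Monthly hazard = −ln(1 − risk)/12. For 10% and 4% the hazard ratio is 0.1054/0.0408 = 2.58. Simulated power:

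| Method | 10% vs 4% | 15% vs 6% |
|---|---|---|
| Log-rank | 68% | 87% |
| Fisher, event yes/no | 62% | not given |
| t-test, observed times | 32% | 56% |
| Wilcoxon, observed times | 21% | 40% |
| t-test, event times only | 6% | 6% |

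At the lower risks the t-test loses 1 − 32/68 = 53% of the log-rank power and Wilcoxon 1 − 21/68 = 69%. At the higher risks the losses are 1 − 56/87 = 36% and 1 − 40/87 = 54%.

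**3. Sensitivity to event rate and follow-up spread.** Here the plan's hazard ratio of 2.19 is borrowed, with follow-up uniform from 48 to 104 weeks (2,000 runs, Monte Carlo error about 1 point):

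| SOC events by week 48 | Log-rank | Fisher | t-test, observed | Wilcoxon, observed |
|---|---|---|---|---|
| 5% | 33% | 24% | 12% | 8% |
| 10% | 58% | 52% | 27% | 19% |
| 20% | 88% | 84% | 64% | 53% |

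Either test on event times only gives 4 to 7% in these scenarios. Over all scenarios run (SOC events 5 to 30%, maximum follow-up 48, 104 or 156 weeks), Fisher loses about 3 to 10 points and 72 to 96% of times are censored. If everyone had exactly 48 weeks, with 10% SOC events, Wilcoxon on observed times would match log-rank (42% each). Its loss therefore comes from the varying follow-up.

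**4. Return to care.** Assumed: 45 LTFU patients in SOC (150 × 0.30) and 22 in ALERT (150 × 0.15 = 22.5, rounded down), return hazard ratio 2.19, SOC median time to return 13, 26 or 52 weeks, and follow-up after LTFU uniform from 0 to 26, 52 or 104 weeks.

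| Median / maximum follow-up (weeks) | Returned | Log-rank, all LTFU | Fisher, proportion | Wilcoxon / t-test, returners |
|---|---|---|---|---|
| 13 / 104 | 85% | 79% | 12% | 53% / 56% |
| 26 / 52 | 53% | 63% | 38% | 13% / 14% |
| 52 / 26 | 20% | 33% | 25% | 3% / 5% |

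Over all nine combinations the ranges are log-rank 33 to 79%, Fisher 12 to 39%, and returners only 3 to 56%. Fisher is weak when nearly everyone returns; the returners-only test is weak when few do. The same follow-up distribution was used in both arms, so these figures show lost power and not any bias from different times at risk.

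**The case against.** **No test is assigned to this outcome.** A reader might infer that the plan prescribes a t-test for time to AIDS or death. It does not. The closing sentence speaks of categorical and continuous variables in general, and cannot fit every item: the list also includes reasons for declining, and those patients were never randomised. Since both other time outcomes get log-rank, a survival analysis may be what the authors intend here too. This stands: the defect is a missing specification.

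**The SAP may settle it.** Section 9.0 calls itself brief and defers to a SAP. That is possible, but it cannot be confirmed from the documents supplied.

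**Most of the power is not lost in every case.** A reader might infer that it is. That is untrue for Fisher, and at 15% against 6% the t-test keeps 56/87 = 64% of the log-rank power. The near-5% result requires dropping everyone without an event, which the text does not ask for. Event rates and accrual time are not in the documents. All of this stands.

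**Return times are not censored.** A reader might infer that they are, or that non-returners are ignored. The gap is defined only for patients who return, so each is fully observed, and the same sentence compares the proportion returning, whose denominator includes non-returners. This stands. What it leaves is the unequal time at risk behind the proportion and the conditioning on return behind the gap.

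**The analyses are descriptive.** This limits the impact but does not remove the point, because arms are to be compared and section 9.6.1 attaches a significance level.

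**Conclusion.** The point holds as an omission. Time to AIDS or death is to be compared between arms under variable follow-up, with no survival method, origin or censoring rule, and the tests that are named do not handle censoring. The size depends on how an analyst fills the gap. Fisher costs about 3 to 10 points. A t-test or Wilcoxon on observed times costs roughly half to three-quarters of the log-rank power when SOC events by week 48 are 5 to 10%, and about 28% (t-test) to 39% (Wilcoxon) at 20%, with follow-up of 48 to 104 weeks. Tests on event times only have almost no power. These figures assume exponential times, proportional hazards, and event rates and accrual spread that the documents do not give. That most AIDS or death times will be censored is plausible, but it is also an assumption.

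For return to care, the two planned comparisons are usable but incomplete. A censored analysis of all LTFU patients uses the information better, with gains that vary widely over the assumed settings. The impact is small: these are other secondary, descriptive analyses, and the primary and main secondary outcomes already have log-rank.

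**What to change.** In section 9.6.4, or in the SAP if it is silent:
- Analyse time to AIDS or death from randomisation by Kaplan-Meier and log-rank, with a Cox model for the hazard ratio, censoring event-free patients at their last data extraction.
- Keep the proportion returning and the gap among returners as description. Add time from LTFU to return in all LTFU patients, with non-returners censored at last data extraction, shown as cumulative incidence by arm. Label it as conditional on post-randomisation LTFU, so that it is not read as a comparison of the groups as randomised. Because LTFU is set at 180 days after the last visit, starting the clock there shifts each gap by a constant and discards nothing.
- Limit Fisher, t-test and Wilcoxon to outcomes without censoring.

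The cost is a few sentences and slightly more analysis work. The remedy uses event, visit and extraction dates that the plan already collects, and leaves sample size and the primary analysis unchanged.

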The ALERT specialist will be responsible for tracking the on-going engagement of patients who are randomized into the intervention arm. Patients will be expected to complete visits at a minimum of every 6 months. However, the ALERT specialist will also review chart notes to review the interval that the provider recommended a medical visit. The ALERT specialist will track that the patient makes and keeps an appointment with their primary provider at the suggested interval. If the patient misses a visit at the recommended interval, the ALERT specialist will perform outreach to schedule a return visit, and again track to see that the visit is kept. The ALERT specialist will use a tracking database in order to track patient engagement, their outreach efforts and delivery of the retention modules. The ALERT specialist will record contacts (categorically) both successful and unsuccessful. They will also utilize the baseline patient contact information as well as other key notes in this tracking database. Patients who meet the LTFU primary end point, regardless of study arm will have outreach activity initiated by the ALERT specialist. This will include following the retention tracking algorithm including evaluating whether the patient is incarcerated, providing outreach calls to the patient, and reviewing the medical record. Patients who meet the primary endpoint and are found to be incarcerated will be removed from the study and censored effective at the time of their incarceration. Those who are incarcerated but then return to care upon release, prior to reaching a primary endpoint will be allowed to remain in study. Patients who are confirmed to have changed care provider to an external health facility (such as a different clinic system or a nursing facility) will be assessed for their current engagement in care; those who have completed a clinic visit with a HIV prescribing clinician within the 180 days will be considered engaged in care, and will not be considered LTFU. The ALERT specialist will request access to the patient's new HIV prescribing provider in order to assess continued follow-up care during the course of the study. In addition, if possible, these patients will continue to come to study site for the annual study visit.

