It is expected that subjects new or returning to care will have regular primary care visits at least 3-4 times in the first year. The ALERT specialist will use the clinic medical record system to abstract data on clinic visits, ART medications, serial HIV RNA and CD4 values, routine CBC and chemistry values, HIV-related and AIDS diagnoses and other medical diagnoses. Data will be entered into the study electronic database. Abstraction will be done at least quarterly for each subject. The ALERT specialist will track the status of each subject and record retention and outreach in the study database. Using data abstracted from the primary care clinic medical records system, the ALERT specialist will record all visits with a prescribing HIV provider, which will document retention as related to the primary study endpoint. For patients in the SOC arm, contact information will be collected for use in the event that the person meets the primary endpoint. Subjects in either arm who reach criteria for the LTFU primary endpoint will be identified by the ALERT specialist. The ALERT specialist will then contact the subject to assure that the patient is not incarcerated or receiving care from an HIV provider at

another facility. Once LTFU is confirmed, the ALERT worker will try to bring the patient in for a primary endpoint visit. All patients will continue to be followed after the primary endpoint (ITT) for assessment of secondary endpoints.

Education Contacts (weeks 1-24). The ALERT specialist will complete a 5 session educational curriculum called a retention module either in person or by phone to the subjects randomized to the ALERT Intervention arm. The 5 retention modules include instruction about the navigation of HIV health systems, HIV literacy, Disclosure, Medication adherence and Continuation with Care, and Self-Efficacy [MOP CCTG 594: 5.0 The 5 Retention Modules for the ALERT specialist]. The goal will be to present the majority of the material within the first 6 months, however scheduling flexibility will be allowed up to the 12 month time-point in order to maximize opportunities for patients to receive the intervention. Subjects that complete all 5 modules will be asked about their reasons motivating them to 1) participate in the study and 2) completing the 5 modules.

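### The between-arm return-to-care analysis in section 9.6.4 is confined to patients who became LTFU, so it is not a randomised comparison of ALERT with SOC and may be biased in either direction

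*Combined protocol and SAP*

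**What the plan says.** Section 9.6.4 (Other Secondary Analyses) introduces the analysis with "For patients who meet the primary endpoint (LTFU) but subsequently return to care" and says that "secondary analyses will measure the proportion returning in the intervention vs. SOC arm". A second measure is "the time between their last and return visit with a prescribing provider". The same section assigns Fisher's exact test to categorical variables and a t-test or Wilcoxon test to continuous ones. Section 9.6.1 treats 0.05 as significant for secondary analyses without multiplicity adjustment, and states the general principle of analysing everyone randomised.

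On what happens at LTFU, section 5.1.4 (Tracking and outreach) says: "Patients who meet the LTFU primary end point, regardless of study arm will have outreach activity initiated by the ALERT specialist". Section 6.2.4 (Data Abstraction) adds "Subjects in either arm who reach criteria for the LTFU primary endpoint will be identified by the ALERT specialist" and "Once LTFU is confirmed, the ALERT worker will try to bring the patient in for a primary endpoint visit". It also says: "All patients will continue to be followed after the primary endpoint (ITT) for assessment of secondary endpoints". Under Ongoing Retention Efforts in that section, continuous monitoring and active re-engagement are described for the intervention arm only.

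**The concern.** Two features stop this from being a randomised comparison.

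- **Selection.** Patients enter the analysis by reaching the primary endpoint. If ALERT changes who reaches it, the LTFU patients in the two arms are different kinds of patient. A difference in their return rates then mixes case mix with any effect of the intervention.
- **Shared outreach.** Return is measured from the point at which SOC patients also begin to receive outreach from the ALERT specialist. The difference in treatment between the arms narrows exactly where the measurement starts.

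The interval from last to return visit is selected once more, because it exists only for those who came back. It also exceeds 180 days by definition.

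At stake is a tested between-arm result that could be reported as ALERT being worse, or better, at re-engagement when it shows neither.

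**Working it through.** **1. The plan's own figure.** Inputs from section 9.4.1 and Table 5: 150 per arm, endpoint-free 70% SOC and 85% ALERT, two-sided alpha 0.05.

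- Hazard ratio = ln(0.70)/ln(0.85) = 2.195 (stated 2.19).
- Expected events = 150 × (0.30 + 0.15) = 67.5.
- Freedman log-rank power = Φ(√67.5 × (2.195 − 1)/(2.195 + 1) − 1.96) = 86.7% (stated 87%).

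The design rates reproduce and can be used for the size of the subset. The plan gives no figure for the return-to-care comparison itself.

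**2. Size of the subset.** SOC: 150 × 0.30 = 45. ALERT: 150 × 0.15 = 22.5.

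**3. Effect of selection.** The documents give no return rates and no split of patients by how easily they can be brought back, so these are assumptions. Easy patients return at 60% and hard patients at 20%, the same in both arms, so ALERT has no effect on return. The 45 SOC losses are taken as 25 easy and 20 hard.

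SOC return among LTFU = (25 × 0.6 + 20 × 0.2)/45 = 19/45 = 42.2%. SOC never LTFU, or LTFU and returned = (105 + 19)/150 = 82.7%.

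Only the make-up of the 22.5 ALERT losses is varied:

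| ALERT mainly prevents | Easy + hard remaining | Returned | Return among LTFU | Never LTFU or returned, of 150 |
|---|---|---|---|---|
| easy losses | 4.5 + 18 | 2.7 + 3.6 = 6.3 | 28.0% | (127.5 + 6.3)/150 = 89.2% |
| both in proportion | 12.5 + 10 | 7.5 + 2.0 = 9.5 | 42.2% | (127.5 + 9.5)/150 = 91.3% |
| hard losses | 18 + 4.5 | 10.8 + 0.9 = 11.7 | 52.0% | (127.5 + 11.7)/150 = 92.8% |

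The subset comparison runs from 14 points against ALERT to 10 points in its favour, with no true effect on return. The measure on all randomised favours ALERT in every row. If easy and hard patients return at the same rate, the subset shows no case-mix bias under any split.

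**4. A real benefit can be masked.** Suppose 15% of patients become LTFU in either arm and return at 30%, and another 15% become LTFU only under SOC and return at 60% (assumed rates). Subset return is then (0.30 + 0.60)/2 = 45% SOC against 30% ALERT. If ALERT truly adds 10 points to return in the first group, the comparison reads 45% against 40%, still 5 points against ALERT.

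**5. Another denominator does not help.** Dividing LTFU-and-returned by all randomised gives, with equal 30% return, 0.30 × 0.30 = 9% SOC against 0.15 × 0.30 = 4.5% ALERT. SOC looks better only because it has more losses.

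**6. Precision.** Exact Fisher rejection probability at 45 against 22 patients, by enumeration: 28.6% for a true 50% against 30%. For the selection-only difference of 42.2% against 28.0% it is about 15%, almost all in favour of SOC.

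**The case against.** The strongest reply is that little harm can follow. Return to care is not among the objectives in section 1.3, and section 9.6.4 calls its analyses descriptive. The randomised comparison of retention is the primary log-rank test, and visits per year is already a planned between-arm measure. This stands as a limit on severity. It does not remove the point, because the same section assigns tests, section 9.6.1 supplies a 0.05 threshold, and nothing warns that the comparison is not randomised.

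Two stronger readings are tempting, and the documents support neither.

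- A reader might infer that the arms are treated identically after LTFU, so that only case mix is left. ALERT-arm patients may already have had up to five modules, and section 6.2.4 reserves the continuing re-engagement effort for them. In SOC the specialist checks for incarceration or care elsewhere and tries to arrange an endpoint visit. That is a study assessment (section 6.2.5) and not necessarily the prescriber visit that counts as return. The contrast is diluted, not abolished.
- A reader might infer that the result will point against ALERT. That needs ALERT to prevent mainly the easier losses. Intensive tracking could equally retain hard-to-reach patients, and the bias then favours ALERT.

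The denominator is also a matter of reading. Taken literally, the sentence describes those who returned, of whom all returned. Patients who became LTFU is the natural meaning, but the plan should say so.

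**Conclusion.** The point holds in a limited form. The return-to-care comparison is conditioned on the primary outcome and starts when SOC patients begin to receive ALERT specialist outreach, so a difference cannot be read as a randomised effect of ALERT. Bias may go either way. In the illustration ALERT shows 28%, 42% or 52% against 42% in SOC, with no true effect on return. Those figures rest on assumed return rates and an assumed easy/hard split. They show what can happen and are not estimates. The subset size of about 45 against 22 to 23 rests on the plan's 70% and 85% rates, and power of about 29% for a 20-point difference (50% against 30%) means the comparison would tell little even if it were unbiased. The primary analysis is not affected. The change should be made because it is cheap and the plan otherwise tests this subset by arm.

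**What to change.** Amend section 9.6.4, and the SAP, which section 9.0 says takes precedence.

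1. **Add a comparison on all randomised participants**, from the prescriber visit dates already abstracted at least quarterly. Use either in care at week 48 (a prescriber visit in the prior 180 days) or the share of follow-up days out of care over the first 48 weeks. Week 48 is the guaranteed minimum follow-up. Use later time points only for participants with enough follow-up, and say so. The never-lost-or-returned share in the working is a simplified stand-in for these measures.
2. **State how removals are counted.** Patients found incarcerated on reaching LTFU leave the study (sections 5.1.4, 8.1.6 and 9.6.2), and others withdraw. Both need a stated rule in the new measure.
3. **Note the dilution.** SOC outreach after LTFU narrows the arm difference in the new measure as well.
4. **Keep return and time to return among LTFU patients as description by arm**, with the denominator stated, no p-value, and a note that the comparison is not randomised and that SOC patients were receiving ALERT outreach by then.

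The cost is analysis-plan wording and one derived variable. Outreach, visits and data collection do not change.
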